5.3. Lifestyle Considerations

Per the Schedule of Activities (Section 1.3), qualified medical staff will provide diabetes management counseling, which will include instructions on diet and exercise and education about the signs, symptoms, and treatment of hypoglycemia, should it occur.

Prescription or OTC medications that promote weight loss are exclusionary if used within 3 months prior to screening (study entry), or between screening and randomization. These medications are also not allowed at any time during the treatment period. If started after randomization, they should be immediately withdrawn.

Study participants should be instructed not to donate blood or blood products during the study or for 4 weeks following the study.

5.3.1. Meals, Dietary Restrictions, and Activity

Patients should continue their usual exercise habits and generally follow a healthy meal plan (with consistent meal size and time of day) throughout the course of the study. Dietary counseling may be reviewed throughout the study, as needed.

In addition, patients should not receive an intensive diet/exercise program with the intent of reducing body weight at any time during the study, other than the lifestyle and dietary measures for diabetes treatment.

5.4. Screen Failures

Screen failures are defined as participants who consent to participate in the clinical study but are not subsequently randomly assigned to study intervention. A minimal set of screen failure information is required to ensure transparent reporting of screen failure participants to meet the Consolidated Standards of Reporting Trials (CONSORT) publishing requirements and to respond to queries from regulatory authorities. Minimal information includes demography, screen failure details, eligibility criteria, and any SAE.

Individuals who do not meet the criteria for participation in this study (screen failure) may be rescreened once. The interval between screening and rescreening should be at least 4 weeks. A new ICF must be signed at the time of rescreening and the study participant will be assigned a new identification number. A single repeat testing of suspected erroneous/spurious central laboratory results is allowed without rescreening the study participant.

6. Study Intervention

[figure not shown]
Study intervention is defined as any investigational intervention(s), marketed product(s), placebo, or medical device(s) intended to be administered to a study participant according to the study protocol.

6.1. Study Intervention(s) Administered

LY3209590 will be provided in a 20 mg vial of lyophilized powder. Upon reconstitution per the pharmacy instructions provided by the sponsor, LY3209590 will be administered once weekly as SC injections. Each patient will receive 1 injection each week, as described in the “Treatment Regimens” table below. Subcutaneous injections of LY3209590 will be administered rotating between left and right abdominal regions, and upper and lower quadrants. Refer to Study Period 2 in Section 4.1.1 for details on how IP will be administered.

Patients will receive treatment with LY3209590 by an algorithm described in Section 10.8.

The LY3209590 Algorithm 1 is a paper-based algorithm that uses similar principals to the established Riddle algorithm.

Insulin degludec will use the established Riddle algorithm and is a paper-based algorithm.

Approximately one-half of the subjects will be randomized in each of the 2 remaining treatment groups.

Insulin degludec will be provided as 100 units/mL in a prefilled pen. It will be administered once daily at approximately the same time of day, rotating between left and right abdominal regions, and upper and lower quadrants.

See Section 6.7.1 for transitioning to treatment after study completion.

Treatment Regimens

Regimen	Dose Randomization through Week 26
LY Dose Algorithm 1 (paper)	LY injection
Insulin degludec	insulin degludec injection (open-label)

Abbreviations: LY = LY3209590.

The investigator or his/her designee is responsible for the following:

- explaining the correct use of the investigational agent(s) to the patient
- verifying that instructions are followed properly
- maintaining accurate records of IP dispensing and collection
- at the end of the study returning all unused medication to Lilly, or its designee, unless the sponsor and sites have agreed all unused medication is to be destroyed by the site, as allowed by local law.

Clinical study materials will be labeled according to the country's regulatory requirements.

6.1.1. Selection and Timing of Doses

For patients randomly assigned to LY3209590, an initial dose will be determined using Table 1 for Algorithm 1 (see Section 10.8). The weekly dose adjustment thereafter will be based on guidance provided in Section 10.8. The doses will be administered at approximately the same time and day each week.

If a patient misses a scheduled dose of LY3209590, it should be administered as soon as possible, but no later than 3 days after the scheduled administration. If more than 3 days have elapsed since the scheduled administration, the dose should be skipped and the next injection will occur at the next scheduled day and time.

Insulin degludec should be administered at the same time each day adjusted per the modified Riddle algorithm (Section 10.8.2).

Patients who miss a dose of insulin degludec should inject their daily dose during waking hours upon discovering the missed dose. Instruct patients to ensure that at least 8 hours have elapsed between consecutive insulin degludec injections (Tresiba® USPI).

The actual date, time and dose of each dose administrations (LY3209590 and insulin degludec) will be recorded in the participant's diary (and participant's medical record when administered at the site).

For details on the titration algorithms to be used, refer to Section 10.8.

6.1.2. Special Treatment Considerations

6.1.2.1. Standards of Medical Care

Investigators and other study team members are expected to treat patients according to the nationally established standards of care for diabetes management in respective participating countries, except where that treatment would be in conflict with the protocol-provided treatment requirements. If there are no local standards of care for diabetes, the investigators should follow current published standards of care from the American Diabetes Association (ADA 2016) and the European Association for Study of Diabetes (Inzucchi et al. 2015) during their patients' participation in this study. Standards of prevention of persistent hyperglycemia and ketone monitoring must be followed during the course of the study to prevent DKA.

This section provides guidance on management of episodes of hypoglycemic events and events of severe, persistent hyperglycemia. For effective implementation of measures described here, it is important that patients, and their caregivers, if applicable, be well-educated about the signs and symptoms of hyperglycemia (for example, severe thirst, dry mouth, frequent micturition, or

dry skin) and hypoglycemia (for example, intense hunger, sweating, tremor, restlessness, irritability, depression, headaches, disturbed sleep, or transient neurological disorders). Patients should be instructed to contact the investigative site in the event of severe, persistent hyperglycemia or severe hypoglycemia between study visits.

6.1.2.2. Management of Increased Hypoglycemia Risk

The allowable oral antihyperglycemic medications (OAMs) are non-secretagogues; therefore, clinically relevant increases in the risk of hypoglycemia due to the OAMs are not expected in this trial. To date, effects of LY3209590 on hypoglycemia are not different as compared to other basal insulins. An objective of the study is to assess the risk of hypoglycemia in insulin naïve T2DM patients receiving LY3209590 as compared to insulin degludec.

In this study, increased risk of hypoglycemia is defined as having a single episode of severe hypoglycemia or having more than 1 episode of documented hypoglycemia within a 1-week period at any time during the treatment period. Documented hypoglycemia is defined as any time a participant reports a SMBG ≤ 70 mg/dL (< 3.9 mmol/L) or any investigator confirmed case of severe hypoglycemia.

In cases where a patient experiences hypoglycemia as described above, to confirm the increased risk, the study sites must ensure that the patient has been fully compliant with the assigned therapeutic regimen and also that there is no evidence of other possible causes of hypoglycemia (e.g., omission of meal, unexpected increase in exercise).

Patients fulfilling the definition of increased risk of hypoglycemia should first decrease their dose of IP per the respective dosing algorithm, followed by discontinuation of IP, if needed. If the patient continues to experience hypoglycemic events after the discontinuation of IP, the investigator should discontinue the patient from OAM therapy.

6.1.2.3. Management of Patients with Severe, Persistent Hyperglycemia During the Treatment Period

An additional therapeutic intervention should be considered in patients who develop severe, persistent hyperglycemia after randomization based on the following criteria (FDA 2008):

- a) average FG > 270 mg/dL (> 15.0 mmol/L) over any 2-week period or longer during the first 6 weeks postrandomization; or
- b) average FG > 240 mg/dL (> 13.3 mmol/L) over any 2-week period or longer from Week 6 to Week 12 postrandomization; or
- c) average FG > 200 mg/dL (> 11.1 mmol/L) over any 2-week period or longer after Week 12.

Investigators should first confirm that the patient does not have an acute condition causing severe hyperglycemia and, after the first 12 weeks of the study, that the patient is fully compliant with the assigned therapeutic regimen. The investigator will decide, in consultation with the patient, on an appropriate glucose-lowering intervention (rescue intervention) after considering relevant clinical criteria. See table in Section 6.5 for allowed medications. Patients who receive a new intervention for hyperglycemia management should also continue administering IP for the remaining period in the trial.

6.1.3. Medical Devices

The sponsor will provide marketed blood glucometers and syringes for subcutaneous injection.

6.2. Preparation/Handling/Storage/Accountability

The investigator or designee must confirm appropriate temperature conditions have been maintained during transit for all study intervention received and any discrepancies are reported and resolved before use of the study intervention.

Only participants enrolled in the study may receive study intervention and only authorized site staff may supply or administer study intervention. All study intervention must be stored in a secure, environmentally controlled, and monitored (manual or automated) area in accordance with the labeled storage conditions with access limited to the investigator and authorized site staff.

The investigator, institution, or the head of the medical institution (where applicable) is responsible for study intervention accountability, reconciliation, and record maintenance (i.e., receipt, reconciliation, and final disposition records).

Further guidance and information for the final disposition of unused study interventions will be provided by the sponsor.

The study site must store all study interventions in a locked and secure environment.

Investigators should consult the study drug information provided in the Pharmacy Instructions provided by the sponsor or label for the specific administration information (including warnings).

6.3. Measures to Minimize Bias: Randomization and Blinding

This is an open-label study; thus, it will be unblinded. However, the specific intervention to be taken by a participant will be assigned using an interactive web–response system (IWRS). The site will contact the IWRS prior to the start of study intervention administration for each participant. The site will record the intervention assignment in the appropriate data capture tool. Potential bias will be reduced by the following steps: central randomization, stratification, blinded adjudication for CV endpoints.

Patients who meet all criteria for enrollment will be randomized to treatment at Visit 3. Assignment to treatment groups will be determined by a computer-generated random sequence using the IWRS. The IWRS will be used to assign IP to each patient. Site personnel will confirm that they have located the correct IP by entering a confirmation number found on the IP label into the IWRS.

To achieve between-group comparability for site factor, the randomization will be stratified by baseline HbA1c (<8.5%, ≥8.5%), DPPIV (yes/no), SGLT2 (yes/no), country, and baseline BMI (<30, ≥30). The randomization scheme will be performed using IWRS, which will ensure balance between treatment groups.

6.4. Study Intervention Compliance

The assessment of treatment compliance with IP (LY3209590 or insulin degludec) will be determined by the following:

- Information about the once weekly IP injections administered at home by the patient will be entered into the patient diary by the patient and reviewed by the site personnel at each study visit; this information will be collected in the electronic study diary;
- IP accountability will be checked according to the Schedule of Activities (Section 1.3). Study participants will be instructed to return all dispensed vials, any *unused* pens and/or all empty cartons at the next visit to the study site for the purpose of performing drug accountability.

Other aspects of compliance will also be assessed at each visit, including the patient's adherence to the visit schedule, compliance with the concomitant OAM requirements and other medication guidances (Section 6.5), completion of study diary, results of SMBG, and any other parameters the investigator considers necessary. Patients considered to be poorly compliant with their medications and/or study procedures (for example, missed visits or specific diagnostic tests) will receive additional training and instructions, as required.

When participants are dosed at the site, they will receive IP directly from the investigator or designee, under medical supervision. The date and time of each dose administered in the clinic will be recorded in the source documents and recorded in the diary.

When participants administer study treatment at home, compliance with study treatment will be assessed at each visit. Compliance will be assessed by direct questioning, counting returned pens, etc. during the site visits.

A record of the number of the pens and study medications dispensed to and taken by each participant must be maintained and reconciled with study intervention and compliance records. Intervention start and stop dates, including dates for intervention delays and/or dose reductions will also be recorded in the eCRF.

6.5. Concomitant Therapy

Any medication or vaccine (including over-the-counter or prescription medicines, vitamins, and/or herbal supplements or other specific categories of interest) that the participant is receiving at the time of enrollment or receives during the study must be recorded in the eCRF along with:

- Reason for use
- Dates of administration including start and end dates, and
- Dosage information including dose and frequency for concomitant therapy of special interest.

In addition, for permitted concomitant glucose-lowering agents, the dosage will also be documented and collected.

Lilly Medical should be contacted if there are any questions regarding concomitant or prior therapy.

Participants will be permitted to use concomitant medications that they require during the study, except prohibited medications described in Section 5.2 and Sections 6.5.1 through 6.5.4 below. In addition, certain permitted medications (for example, treatments for blood pressure or dyslipidemia) described in Sections 6.5.5 and 6.5.6 should be continued, but not changed, during the study.

Investigative site staff will inform patients that they must consult with the investigator or a designated site staff member upon being prescribed any new medications during the study, except when initiated for treatment of medical emergencies.

Non-study medications taken by patients who are screened but not randomized will not be reported to Lilly unless an SAE or AE occurs that the investigator believes may have been caused by a study procedure.

The table below provides a summary of criteria for use of concomitant medications that may interfere with planned assessments during the study.

Criteria for Use of Concomitant Medications that may Interfere with Efficacy and Safety Assessments in Study BDCL

Drug Class	Use During Screening/Lead-In	Conditions for Use After Randomization		
		Acute Therapy ^a	Rescue Therapy	During Safety Follow-up Period
Drugs with approved weight loss indication ^b	Prohibited	N	N/A	N
Systemic glucocorticoid therapy ^c	Excluded except for acute therapy ^a	Y	N/A	N
Antihyperglycemia medications				
GLP-1 RAs	Prohibited	N	N	Y
DPP-4 inhibitors	Permitted	N	Y	Y
SGLT2 inhibitors	Permitted	N	Y	Y
SC Insulins and insulin mixtures	Prohibited except for acute therapy ^a	Y	Y	Y
Inhaled insulins	Prohibited	N	N	N
Meglitinides	Prohibited	N	Y	Y
Alpha-glucosidase inhibitors	Prohibited	N	N	Y
Sulfonylureas	Prohibited	N	Y	Y
Thiazolidinediones	Prohibited	N	N	N
Metformin ^d	Required	N	Y ^e	Y

Abbreviations: DPP-4 = dipeptidyl peptidase-4; GLP-1 RA = glucagon like peptide-1 receptor agonist; N = no; N/A = not applicable; SC = Subcutaneous; SGLT2 = sodium-glucose cotransporter 2; Y = Yes.

- a Acute therapy = treatment for up to 14 days.
- b Includes Saxenda® (liraglutide 3.0 mg), Xenical® (orlistat), Meridia® (sibutramine), Sanorex® (mazindol), Adipex-P® (phentermine), Belviq® (lorcaserin), Qsymia® (phentermine/topiramate combination), Contrave® (naltrexone/bupropion) or similar other body weight loss medications including over-the-counter medications (e.g., alli® [orlistat 60 mg capsules]).
- c Does not apply to topical, intraocular, intranasal, intraarticular, or inhaled preparations;
- d Switching metformin manufacturers is allowed, as long as the dosage is the same. Changing to a metformin formulation with a different action profile (i.e., from short-acting to long-acting metformin) is not permitted.
- e For rescue therapy, metformin dose may be increased if the dose is below maximum approved dose per country-specific label.

6.5.1. Antihyperglycemia Medications

The only glucose-lowering agents allowed as rescue therapy during the study are concomitant metformin, SLGT-2 inhibitors, DPP-4 inhibitors, meglitinides, sulfonylureas and insulin. In addition, short-term insulin use (up to 14 days) for management of medical emergencies is allowed prior to study entry and during the study. Rescue therapy with other glucose-lowering agents may be medically indicated in certain situations after randomization (see table in Section 6.5). These situations are described in Section 6.1.2.3 (severe, persistent hyperglycemia) and in Section 7.1.1 (permanent discontinuation of IP).

If any new glucose-lowering medication is initiated after randomization at Visit 3, other than IP, rescue therapy, or short-term use of insulin for medical emergencies, the patient will be required to immediately discontinue the medication and the appropriate study deviation report will be generated. Any such violation of the protocol that lasts longer than 14 days will exclude the patient from the per-protocol population for analyses.

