6.5.4. Systemic Glucocorticoids

Chronic systemic glucocorticoid therapy (excluding topical, intraocular, intranasal, or inhaled preparations) is exclusionary if used >14 consecutive days during the 1-month period before screening or between screening and randomization at Visit 3.

Patients treated with these medications after randomization will be excluded from the efficacy evaluable population for analyses if they receive:

- >14 days consecutive days of therapy, or
- More than one course of therapy during the study.

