9.3. Populations for Analyses

The following populations are defined:

Population	Description
Entered/Enrolled Population	All participants who sign the ICF
Randomized Population	All participants assigned to treatment, regardless of whether they take any doses of study treatment, or if they took the correct treatment. The participants previously randomized to Algorithm 2 will be pooled with the participants randomized to Algorithm 1 and all of these participants will be analyzed as one treatment group of LY3209590.
Efficacy Population	Participants in randomization population excluding the participants previously randomized to Algorithm 2.
Safety Population	All participants randomly assigned to study treatment and who take at least 1 dose of study treatment. The participants previously randomized to Algorithm 2 will be pooled with the participants randomized to Algorithm 1 and all of these participants will be analyzed as one treatment group of LY3209590.
Pharmacokinetic Population	All randomized participants who received at least 1 dose of LY3209590 and have at least 1 evaluable PK sample.

Abbreviations: ICF = informed consent form; PK = pharmacokinetics.

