9.4.3. Primary endpoint(s)

The primary objective is to compare the HbA1c change from baseline to Week 26 between LY3209590 treatment and insulin degludec. It is intended to estimate the treatment differences in the change in HbA1c from baseline to 26 weeks if participants adhered to the treatment without intercurrent events (stop of the study medication and/or use of rescue medication). It is a type of hypothetical estimand based on International Council for Harmonisation (ICH) E9(R1). Only data before the occurrence of the intercurrent events (use of rescue medication or stop of the study medication) will be included in the analysis and the resulting missing values will be imputed implicitly in the mixed-effect model for repeated measurements (MMRM) analysis. The MMRM model will include treatment, strata (country, DPPIV [yes/no], SGLT2 [yes/no] and baseline BMI [<30 , ≥ 30]), visit, and treatment by visit interaction as fixed factors and the baseline of the dependent variable as a continuous covariate.

As a sensitivity analysis, the treatment differences in HbA1c change from baseline to Week 26, only if patients could complete the treatment, will also be estimated. More details will be specified in the SAP.

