ICF	informed consent form
ICH	International Council for Harmonisation
IMP	Investigational Medicinal Product
Informed consent	A process by which a participant voluntarily confirms his or her willingness to participate in a particular study, after having been informed of all aspects of the study that are relevant to the participant's decision to participate. Informed consent is documented by means of a written, signed and dated informed consent form.
INR	international normalized ratio
IP: investigational product	A pharmaceutical form of an active ingredient or placebo being tested or used as a reference in a clinical trial, including products already on the market when used or assembled (formulated or packaged) in a way different from the authorized form, or marketed products used for an unauthorized indication, or marketed products used to gain further information about the authorized form.

interim analysis	An interim analysis is an analysis of clinical study data, separated into treatment groups, that is conducted before the final reporting database is created/locked.
IRB/IEC	Institutional Review Boards/Independent Ethics Committees
ISR	injection site reaction
ITT	intention to treat: The principle that asserts that the effect of a treatment policy can be best assessed by evaluating on the basis of the intention to treat a participant (that is, the planned treatment regimen) rather than the actual treatment given. It has the consequence that participant allocated to a treatment group should be followed up, assessed, and analyzed as members of that group irrespective of their compliance to the planned course of treatment.
IWRS	interactive web-response system
MAD	multiple-ascending dose
NAFLD	non-alcoholic fatty liver disease
NIM	non-inferiority margin
NIMP	Non-investigational Medicinal Product
OAM	oral antihyperglycemic medications
OTC	over the counter
participant	Equivalent to CDISC term “subject”: an individual who participates in a clinical trial, either as recipient of an investigational medicinal product or as a control
PC	product complaint
PK/PD	pharmacokinetics/pharmacodynamics
PPS	per-protocol set: The set of data generated by the subset of participant who sufficiently complied with the protocol to ensure that these data would be likely to exhibit the effects of treatment, according to the underlying scientific model.
PRO/ePRO	patient-reported outcomes/electronic patient-reported outcomes
QTc	corrected QT interval
SAD	single-ascending dose

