5.1. General Considerations

All data will be entered, verified, and archived at a contract research organization (CRO) external to Eli Lilly and Company (Lilly) and/or at Lilly. Data listings, summaries, and analyses will be performed by a CRO and/or by Lilly under the guidance and approval of statisticians at Lilly.

Statistical analysis of this study will be the responsibility of sponsor or its designee. Any change to the data analysis methods described in the protocol will require an amendment only if it changes a principal feature of the protocol. Any other change to the data analysis methods described in the protocol, and the justification for making the change, will be described in this SAP and/or the clinical study report (CSR). Additional exploratory analyses of the data will be conducted as deemed appropriate.

The following populations are defined for purpose of analysis:

Population	Description
Entered/Enrolled Population	All participants who sign the ICF
Randomized Population	All participants assigned to treatment, regardless of whether they take any doses of study treatment, or if they took the correct treatment. The participants previously randomized to LY3209590 Algorithm 2 will be pooled with the participants randomized to Algorithm 1 and all of these participants will be analyzed as one treatment group of LY3209590.
Efficacy Population	All participants randomized to either LY3209590 Algorithm 1 or insulin degludec and took at least 1 dose of study treatment. Participants will be analyzed according to the treatment they were assigned.
Safety Population	All participants randomly assigned to study treatment and who took at least 1 dose of study treatment. The participants previously randomized to LY3209590 Algorithm 2 will be pooled with the participants randomized to Algorithm 1 and all of these participants will be analyzed as one treatment group of LY3209590.
Pharmacokinetic Population	All randomized participants who received at least 1 dose of LY3209590 and have at least 1 evaluable PK sample.

Abbreviations: ICF = informed consent form; PK = pharmacokinetics.

Unless otherwise stated, the efficacy analyses will be conducted on efficacy analyses set (EAS) based on Efficacy Population using the data up to the study treatment discontinuation (defined as

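### Two protocol rules exclude patients with prolonged prohibited medication from analysis populations that are never defined as such, and no planned analysis applies either rule or tests its effect on HbA1c

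*Protocol*

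**What the plan says.** Two sections on concomitant therapy carry analysis rules.

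- Protocol 6.5.4, on systemic glucocorticoids: "Patients treated with these medications after randomization will be excluded from the efficacy evaluable population for analyses if they receive" more than 14 consecutive days of therapy, or more than one course during the study.
- Protocol 6.5.1, on new glucose-lowering drugs "other than IP, rescue therapy, or short-term use of insulin for medical emergencies": the drug must be stopped at once and a deviation report filed. It then adds: "Any such violation of the protocol that lasts longer than 14 days will exclude the patient from the per-protocol population for analyses".

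The populations are set elsewhere. Protocol 9.3 and SAP 5.1 both list five: Entered/Enrolled, Randomized, Efficacy, Safety and Pharmacokinetic. The Efficacy Population is "Participants in randomization population excluding the participants previously randomized to Algorithm 2" in protocol 9.3, and "All participants randomized to either LY3209590 Algorithm 1 or insulin degludec and took at least 1 dose of study treatment" in SAP 5.1. Neither definition mentions concomitant medication. The protocol's abbreviation list has a generic entry, "per-protocol set: The set of data generated by the subset of participant who sufficiently complied with the protocol", but no analysis refers to it.

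Protocol 9.4.3 targets the Week 26 HbA1c difference "if participants adhered to the treatment without intercurrent events (stop of the study medication and/or use of rescue medication"), and uses only data from before those events. SAP 5.7 uses data up to discontinuation of study treatment.

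**The concern.** The protocol singles out two kinds of exposure as serious enough to remove a patient from an efficacy analysis, and the analysis plan then never acts on that. The primary estimand is hypothetical: the effect had patients adhered without intercurrent events. HbA1c measured during weeks of a non-permitted glucose-lowering drug, or during a long steroid course, is a poor stand-in for that. The comparison is also a non-inferiority one in an open-label trial whose study team is unblinded (SAP 6). If the two rules are still unresolved at database lock, someone will have to decide, knowing treatment, whether they apply.

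**Working it through.** **1. Can either rule be carried out as the plan stands?**

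| Item | 6.5.4 glucocorticoids | 6.5.1 non-permitted glucose-lowering drug |
|---|---|---|
| Population named | efficacy evaluable | per-protocol |
| Defined in protocol 9.3 or SAP 5.1 | no | no (generic glossary entry only) |
| Used in a planned analysis | no | no |
| Removed by the Efficacy Population | no | no |
| Counts as rescue | no (protocol 6.5 table: not applicable) | no (excluded by the rule's own wording) |
| Counts as stopping study drug | not in itself | not in itself |
| Covered by a sensitivity analysis | no | no |

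The last row rests on two places. The only analysis in the SAP that drops data for deviations (5.1) is optional and concerns the dose algorithm. The supportive estimand in SAP 5.7 ignores rescue use and treatment status, so it keeps these values by design. HbA1c collected on study drug during such exposures therefore enters the primary MMRM (Weeks 6, 12, 16 and 26), and no planned analysis takes it out.

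**2. The plan's own power figure.** Inputs from protocol 9.2: 100 completers per arm, SD 1.1, margin 0.4, true difference 0, two-sided alpha 0.1 (one-sided 0.05 for non-inferiority).

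- SE = 1.1 × √(2/100) = 0.156
- Power = Φ(0.4/0.156 − 1.645) = 82.3%

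This agrees with the stated figure of more than 80%.

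**3. Possible size of the effect.** The documents give neither the frequency of these exposures nor their effect on HbA1c, so both are assumed here. Shift in the difference (LY3209590 minus degludec) = p(LY) × s(LY) − p(deg) × s(deg), where p is the share of an arm affected and s the change in HbA1c, negative for a glucose-lowering drug. Put all cases in one arm and let b be the size of the shift:

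- Lowered values in the LY3209590 arm: chance of a false non-inferiority claim at a true difference of 0.4 = Φ(b/0.156 − 1.645).
- Lowered values in the degludec arm: power at a true difference of 0 = Φ((0.4 − b)/0.156 − 1.645).

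| Share × effect | b | b / margin | False claim, cases in LY3209590 arm (nominal 5.0%) | Power, cases in degludec arm (planned 82.3%) |
|---|---|---|---|---|
| 2% × 0.5 | 0.01 | 2.5% | 5.7% | 80.6% |
| 2% × 1.0 | 0.02 | 5% | 6.5% | 78.8% |
| 5% × 0.5 | 0.025 | 6.3% | 6.9% | 77.8% |
| 5% × 1.0, or 10% × 0.5 | 0.05 | 12.5% | 9.3% | 72.7% |
| 10% × 1.0 | 0.10 | 25% | 15.8% | 61.2% |

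For glucocorticoids, taken to raise HbA1c, the two arms swap roles. With equal shares and equal effects in both arms, the shift is zero.

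**4. Cost in precision of applying the rules.** If 2%, 5% or 10% of completers in each arm dropped out of the comparison, power would be 81.6%, 80.5% or 78.7%. It passes below 80% at about 7% (93 per arm, 79.8%). Setting only the affected visits to missing in an MMRM should cost no more than this, because earlier HbA1c values stay in.

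**The case against.** Several stronger readings are tempting, and the documents do not support them.

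- *These patients are in the primary analysis because the per-protocol population was never defined.* This does not follow. The primary analysis uses the Efficacy Population (protocol 9.4.1, SAP 5.7), so a properly defined per-protocol set would have removed nobody from it. What 6.5.1 lacks is a supportive analysis.
- *The SAP does the opposite of the protocol.* This fits the glucocorticoid rule at most. There, the efficacy evaluable population has no counterpart except the Efficacy Population, which keeps the patients.
- *The contamination favours non-inferiority.* This holds only for some combinations of arm and drug. A glucose-lowering drug in the degludec arm, or a steroid in the LY3209590 arm, works against the claim, and balanced use largely cancels.

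The other side also has good points on size. The glucose-lowering group is narrow: rescue agents and short-term emergency insulin fall outside the rule, other new agents must be stopped, and protocol 7.2 provides for withdrawal from the study before another effective agent is introduced. That limits the cases but does not remove them, since 6.5.1 itself foresees violations beyond 14 days and 7.2 does not address glucocorticoids. An exposure long before Week 26 may hardly affect the endpoint. Both arms titrate to the same fasting glucose target, so dose changes could offset part of any effect. Deviations and concomitant medications are summarised by arm (SAP 5.4, 5.6), so an imbalance could be seen, though these tables do not show what it does to the treatment difference.

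Finally, adding intercurrent events to the primary estimand is a design choice that the text does not compel. That objection stands, and the change proposed here leaves the primary estimand alone.

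**Conclusion.** The point holds as a gap between stated rules and planned analyses. Protocol 6.5.1 and 6.5.4 promise exclusions that the plan cannot carry out as written; the 6.5.4 rule plausibly conflicts with the population used for the primary analysis; and nothing planned shows whether the non-inferiority conclusion depends on these values. This part rests on the text alone.

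The numerical effect is not known. The shift of 0.01 to 0.10 points rests wholly on assumed shares (2% to 10%) and effects (0.5 to 1.0 points) confined to one arm, with no offset from titration. Its upper end needs one in ten patients of a single arm to be affected by a full point. If such violations are rare, the effect is probably small. A reader should not infer that the primary result is biased, or in which direction.

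**What to change.** Before database lock:

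1. Add to SAP 5.1 and 5.7 a pre-specified sensitivity analysis that repeats the primary MMRM and the comparison with the 0.4 margin, with HbA1c set to missing from the start of any exposure that meets the 6.5.1 or 6.5.4 limits. State how that start is dated, for example as the first day of the course that breaches the limit. Repeating the model in a per-protocol set defined by the same rules would also serve, but it discards whole patients on post-randomization behaviour.
2. Align the population names in protocol 6.5.1 and 6.5.4 with protocol 9.3 and SAP 5.1, so that each rule points to an analysis that exists.
3. In the same edit, state in SAP 5.7 how HbA1c after rescue is handled. Protocol 9.4.3 excludes it, but SAP 5.7 names only discontinuation of study treatment.

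The cost is one derivation from concomitant-medication start and end dates that protocol 6.5 already collects, one further model run, and a few observations lost in the sensitivity analysis only. The primary analysis, the sample size and patient management stay as they are.
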